## **Statistical analysis:**

Data will be analyzed using SPSS (statistical package for social sciences) version 22. Qualitative data will be presented as number and percent, Quantitative data will be tested for normality by Kolmogrov-Smirnov test then described as mean and standard deviation for normally distributed data and median and range for non-normally distributed. The appropriate statistical test will be applied according to data type with the following suggested tests : Chi-Square for categorical variable , Student t test and Mann Whitney U test for continuous variables.

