### Sample size:

Using G power program version 3.1.9.7 to calculate sample size based on expected effect size of 2.02 (  $1.56 \pm 0.52$  &  $0.69 \pm 0.32$  ) depending ,using 2-tailed test ,  $\alpha$  error =0.05 and power = 95.0% , the total calculated sample size will be 16 divided into two groups.

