## **Randomization:**

Each patient will be joined either to group A or B immediately after tooth extraction procedure through a random lottery mechanism (a startup number of 16 pre-printed paper for the first patient lottery, half of them with Platelet-rich fibrin (PRF) and the other with Advanced platelet-rich fibrin (A-PRF) with a probability of 50%) and the offending patient will choose the pre-printed paper with the specific procedure randomly and blindly.

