## **Surgical Procedures:**

After administration of Local anesthesia, gentle atraumatic extraction is performed for the nonrestorable tooth, followed by careful cleaning of the extraction socket. Drilling for the implant begins to create the correct depth and diameter for implant placement. The implant is installed according to manufactures instructions, ensuring proper seating and stability to promote integration with the surrounding bone.

**For Group A,** PRF preparation involves collecting 20 mL of venous blood into anticoagulant-free tubes, followed by centrifugation at 2,700-3,000 RPM for 8-12 minutes. This process separates the blood into layers, from which the fibrin clot is carefully extracted.

**For Group B,** A-PRF is prepared similarly but centrifuged at a lower speed (1300-1500 RPM) for 12-14 minutes to yield a higher concentration of platelets and leukocytes. After preparation.

PRF and A-PRF are applied to the implant site to aid tissue regeneration and integration. Application of Gelatin Sponge to cover the implant before suturing over the implant.

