## 2) Radiographic evaluation:

**A) Marginal Bone Loss:** A CBCT measurement will be done at immediate post-operative and after 6 months will also help assess the amount of marginal bone loss around the implant, which is a critical indicator of implant success. Measurements can be taken from the implant-abutment junction to the crest of the surrounding bone

**B) Buccal/Lingual plate of bone thickness:** A CBCT measurement will be done at immediate post-operative and after 6 months.

The measurement involves identifying the midpoint of the implant and drawing a perpendicular line from this point to the outer buccal cortical plate. This measurement helps evaluate the amount of buccal bone that remains after implant placement and is essential in predicting long-term implant stability and success, as thinner buccal bone can be more prone to resorption

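### Only unadjusted two-sample tests are suggested for the two CBCT outcomes, and for plate thickness the protocol does not fix whether arms are compared on the 6-month value or on the change

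*Protocol*

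**What the plan says.** The Statistical analysis section of the protocol offers, as suggestions to be applied by data type, the chi-square test for categorical variables and "Student t test and Mann Whitney U test for continuous variables". No covariate-adjusted method is listed.

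The Radiographic evaluation section has two outcomes, and for each "A CBCT measurement will be done at immediate post-operative and after 6 months". For item A the scans are to "help assess the amount of marginal bone loss around the implant", so the quantity of interest is a change. For item B, plate thickness, the measurement consists of "drawing a perpendicular line from this point to the outer buccal cortical plate", and its purpose is put this way: "This measurement helps evaluate the amount of buccal bone that remains after implant placement". The section does not say which quantity is compared between arms.

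On timing, the Randomization section states: "Each patient will be joined either to group A or B immediately after tooth extraction procedure through a random lottery mechanism". Under Surgical Procedures, implant placement comes after extraction, and then "PRF and A-PRF are applied to the implant site to aid tissue regeneration and integration". The immediate post-operative scan is therefore taken after allocation.

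**The concern.** Each CBCT outcome has an early value on the same implant that probably predicts the 6-month value. The suggested tests can use it only by subtraction, or not at all. Which of the two is more precise depends on the correlation between scans, which the protocol does not give: subtraction loses when the correlation is low, and ignoring the first scan loses when it is high. With 8 patients per arm, the standard error of the chance difference in mean first-scan value is sqrt(2/8) = 0.5 SD, so a difference above 0.5 SD arises in about 32% of trials.

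For plate thickness there is a second problem. Two scans suggest a change, and a description in terms of remaining bone can be read as a level. Both comparisons stay open until the data are seen, and in a trial of 16 they can easily disagree.

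**Working it through.** **The plan's own figure.** The Sample size section gives 1.56 ± 0.52 and 0.69 ± 0.32, effect size 2.02, two-sided alpha 0.05 and power 95%, and concludes that "the total calculated sample size will be 16 divided into two groups". The pooled SD is sqrt((0.52² + 0.32²)/2) = 0.432, and 0.87/0.432 = 2.015. The noncentral t distribution at 2.02 gives 93.4% power with 7 per arm and 96.3% with 8. The total of 16 is reproduced and is consistent with an unadjusted t test.

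**Assumptions that the protocol does not supply.** Correlation r between the two scans, shown over a range; equal SDs at both scans; normality; no effect of the arm on the first scan.

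**Variance of the arm difference, n = 8 per arm, in SD² units.**
- 6-month value: 2/8 = 0.250
- Change: (2/8) × 2(1 − r) = 0.5(1 − r)
- ANCOVA: (2/8)(1 − r²)(1 + 1/12), where 1/12 is the price of estimating the slope

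| r | 6-month | Change | ANCOVA | ANCOVA vs 6-month | ANCOVA vs change |
|---|---|---|---|---|---|
| 0.3 | 0.250 | 0.350 | 0.246 | −1% | −30% |
| 0.5 | 0.250 | 0.250 | 0.203 | −19% | −19% |
| 0.7 | 0.250 | 0.150 | 0.138 | −45% | −8% |
| 0.8 | 0.250 | 0.100 | 0.0975 | −61% | −2.5% |
| 0.9 | 0.250 | 0.050 | 0.0515 | −79% | +3% |

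**Power (6-month / change / ANCOVA).** Noncentral t with 14, 14 and 13 df. The effect is in SDs of the 6-month value. Reading 2.02 this way is an assumption, because the protocol does not name the outcome behind it.

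| r | Effect 1 SD | Effect 2.02 SD |
|---|---|---|
| 0.3 | 0.46 / 0.35 / 0.46 | 0.963 / 0.887 / 0.964 |
| 0.5 | 0.46 / 0.46 / 0.54 | 0.963 / 0.963 / 0.985 |
| 0.7 | 0.46 / 0.67 / 0.70 | 0.963 / 0.998 / 0.999 |
| 0.8 | 0.46 / 0.84 / 0.84 | 0.963 / 1.000 / 1.000 |

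**Where ANCOVA loses.** If the first-scan SD is s times the 6-month SD, the relative variances are 1 + s² − 2rs for the change and (1 − r²)(13/12) for ANCOVA. At s = r the change has 1 − r², so ANCOVA is 13/12 − 1 = 8.3% worse. For example, s = r = 0.5 gives 0.75 against 0.8125. With equal SDs, ANCOVA is 5.6% worse than the change at r = 0.95 (0.1056 against 0.100, relative to the 6-month value). It is 4% worse than the 6-month value at r = 0.2 (0.96 × 13/12 = 1.04).

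**Open contrast for plate thickness.** This was simulated with 200,000 trials per setting, 8 per arm, r = 0.3 to 0.9. The t test on the 6-month value and the t test on the change reach different conclusions in 31% to 53% of trials at 1 SD, 20% to 28% at 1.5 SD and 4% to 11% at 2.02 SD. Under no effect each test alone holds 5%. If both were run and either could be claimed, the rate would be about 9% to 10%.

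**First scan after allocation.** Suppose implant position differs systematically between arms by 0.5 SD in both scans, with no true effect. The bias is 0.50 SD for the 6-month value, (1 − r) × 0.5 = 0.35 to 0.05 SD for ANCOVA (r = 0.3 to 0.9), and 0 for the change. False-positive rates are about 15%, 9.8% to 5.5%, and 5%.

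**The case against.** The strongest reply is that nothing here is stated wrongly. A t test on either quantity is valid in a randomised trial, the sample size was computed for that test, the list is only suggested, and covariate adjustment is often settled in an analysis plan, which may exist. Validity and the sample size stand as said, and an unseen plan may already repair this. But the protocol does name its tests, and none of them leads to an adjusted comparison.

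Second, the gain is limited. Marginal bone loss is already a change, and against the change ANCOVA gains only 8% at r = 0.7 and 2.5% at r = 0.8. At 2.02 SD there is little power left to win. This stands. The precision figures also rest on equal SDs and an assumed r.

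Third, the phrase about remaining bone may be general rationale and could describe the first scan as well. That is fair: it does not point to a 6-month comparison. It does not settle the contrast either.

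Fourth, the covariate is measured after allocation, and both measurements are taken from the implant. ANCOVA is therefore more exposed than the change to a difference in implant position, though less exposed than the 6-month value. This stands and shapes the remedy.

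A reader might also infer that the planned analysis is biased, or that its false-positive rate is 9% to 10%. The documents support neither. The second figure needs both tests to be run and either to be claimed, and the protocol does not say that will happen.

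**Conclusion.** The point holds as an inexpensive improvement and not as an error of validity. The protocol suggests only unadjusted tests for two outcomes that each have an early scan, and it leaves the plate-thickness comparison open. With 8 per arm, equal SDs and r between 0.5 and 0.8, adjustment lowers the variance by 19% to 61% against the 6-month value and by 19% to 2.5% against the change. The benefit falls mainly on plate thickness and on effects smaller than the planned 2.02 SD. Because r is not given, the practical advantage of ANCOVA is that it stays close to the better unadjusted comparison without r having to be known. It is not always the best of the three and can be up to about 8% less precise than the better one. The part that most needs settling is a single stated contrast for plate thickness.

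**What to change.** In the Statistical analysis section, state that each CBCT outcome is compared by ANCOVA of the 6-month value on arm, with the immediate post-operative value as covariate, and that the adjusted difference is reported with its 95% CI. ANCOVA of the change with the same covariate gives the identical arm difference, so marginal bone loss can still be reported as a loss.

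Name a t test on the change as the sensitivity analysis, with Mann-Whitney only if the data are clearly non-normal. The two analyses then differ only in how the first scan is used, and a disagreement can be interpreted.

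Report the immediate post-operative values by arm. State the assumption that neither the material nor the allocation affects that first scan, implant position included, because the scan follows randomisation.

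The cost is wording, on data already collected, and 1 of 14 residual degrees of freedom. Precision may be up to about 8% lower than with the better unadjusted comparison if the correlation is very low or the SD ratio happens to equal r. The exposure to a systematic difference in implant position is greater than with the change alone.

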## **Ethical Considerations:**

- The study will adhere to the Declaration of Helsinki and obtain ethical approval from the [Faculty of Oral and Dental Medicine, Delta University].
- Informed consent will be obtained from all participants.
- Patient confidentiality and data security will be maintained throughout the study.
- Before starting our proposal, the sample size is calculated by the G-power analysis software for power and significance
- After the study, the collected data will be extracted and statistically analyzed using statistical package for social science software (SPSS)

## **Estimated time:**

- The estimated time will be 9 months.

## **Estimated cost:**

- The estimated cost will be about 300,000 EGP.

